8.2 Rationale for study design

The design of the study is based on the aim to study safety, tolerability, PK and PD of selected doses of GS-248 in a limited number of healthy volunteers and patients. The design is adaptive, to allow for flexible dose escalation and involves careful monitoring of the subjects' well-being. The time points for PK blood sampling have been selected based on data obtained from pre-clinical studies but may be changed based on emerging data. Time points for PD sampling (blood and urine) is based on previous experience with selective inhibition of the mPGES-1 in a human Phase I study [15] and on predicted human PK.

A placebo control will be used in Parts I, II and III to establish the frequency and magnitude of changes in endpoints that may occur in the absence of active treatment.

Randomisation will be used in Part I, II and III to minimise bias in the assignment of subjects to dose groups and to increase the likelihood that known and unknown subject attributes (e.g., demographic and baseline characteristics) are evenly balanced across treatment groups.

Blinded treatment will be used in Part I, II and III to reduce potential bias during data collection and evaluation of endpoints.

Part IV will be non-placebo controlled, non-randomised and open. The purpose of Part IV is to collect PD data for comparison with GS-248.

Overall, the study will provide important data to support the design of further studies, both in healthy volunteers and in patients.

8.3 Selection of starting dose and rationale for planned dose escalation

8.3.1 Selection of starting dose in the SAD part

A single oral dose of 1 mg is proposed for the first cohort, since it is estimated that this will yield a pharmacological response close to the Minimum Anticipated Biological Effect Level (MABEL), which corresponds to 20% of the maximum attainable area under the effect (AUE; i.e. inhibition) curve 0-24 h as described in the IB.

In assessment of the pharmacological response in terms of mPGES-1 inhibition, one must consider both the duration and the magnitude of such inhibition, i.e. the AUE. In view of a target human dosing interval of at most 24 h and the projected PK of GS-248, it appears reasonable to apply the AUE from 0 to 24 h [$AUE_{(0-24)}$] as a function of dose in order to define MABEL. In this context, 20% of maximum attainable $AUE_{(0-24)}$ is chosen to constitute MABEL, and is projected to be achieved by a single oral dose of GS-248 between 0.9 and 1.7 mg, based on allometric scaling from dog and cynomolgus monkey, respectively.

The NOAEL in the 28-day dog toxicity study was set at 20 mg/kg, with mean C_{max} and $AUC_{0-24 h}$ values at this dose level of 2500 nmol/L and 23000 h*nmol/L (in males and females combined), respectively. These values set the maximum limits for exposure in humans in this Phase I study.

The predicted exposure at the chosen starting dose in the SAD phase results in exposure margins for C_{max} and $AUC_{0-24 h}$ of 250- and 290-fold, respectively, compared to the exposure at the lowest dose level in the dog study, and 450- and 740-fold, respectively, compared to the

exposure at the NOAEL (Table 8.3-1). All these margins are considered to constitute good safety margins between animals and man. However, it should be realised that the human exposure values used in these calculations are, of necessity, only estimated values.

Table 8.3-1 Exposure margins for mean C_{max} and AUC_{last} values between GS-248-treated animals in the pivotal 28-day toxicity studies and the predicted values in humans in the SAD

| Species | Study No. | Dose level (mg/kg animals) (mg humans) | Duration (days) | Sex | C_{max} (nmol/L) | AUC^a (h*nmol/L) | Exposure margin animals:man ^e (X-fold) | |
|---------|------------|--|--------------------|----------------|-----------------------|------------------------|---|------------------|
| | | | | | | | C_{max} | AUC^a |
| Rats | 36325 | 150/400/1000 (< NOAEL) | 28 | F ^b | ca. 2100 ^c | ca. 30000 ^c | - | - |
| Dogs | 36327 | 5 | 28 | M+ F | 1400 | 9000 | - | - |
| | | 20 NOAEL | 28 | M+ F | 2500 | 23000 | - | - |
| Humans | Pre-dicted | 1 Starting dose SAD ^d | 1 | - | 4.6-5.6 | 19-31 | 250 ^f | 290 ^f |
| | | | | | | | 450 ^g | 740 ^g |

NOAEL = No observed adverse effect level

a AUC_{0-24h} in rats and dogs; $AUC_{0-\infty}$ in humans

b Exposure was clearly higher in female rats than in males. Therefore, values in females only are included exposure

c Exposure was equivalent at all 3 dose levels in rats. Therefore, approximate mean values from all females combined are given

d See above in Section 8.3.1 for the rationale for the starting dose in the SAD phase of the study

e All exposure margins are calculated against the highest predicted exposure values in man

f Exposure margins based on the lowest dose level in the 28-day dog study

g Exposure margins based on NOAEL (the intermediate dose level) in the 28-day dog study

Additionally, an approximate comparison of the given doses in the preclinical repeat-dose studies expressed as mg/m^2 body surface area can be used to supplement comparison based on kinetic data. The mg/kg doses are converted to mg/m^2 body surface area by multiplying by a factor 20 for dogs and 37 for a 60 kg human in terms of Human Equivalent Dose (HED), as per FDA guideline on estimation of maximum safe starting dose in initial clinical trials [17].

This gives $0.62 mg/m^2$ for the starting dose in the SAD part (1 mg) $100 mg/m^2$ for the lowest dose level (5 mg/kg) and $400 mg/m^2$ for NOAEL (20 mg/kg) in the 28-day dog study, with dose margins of 160- and 650-fold, respectively.

In view of the sizable margin against NOAEL in the 28-day dog study in terms of predicted human $AUC_{(0-inf)}$ (740-fold) and also in terms of HED (650-fold), together with the fact that the target, mPGES-1, has previously been subject to pharmacological intervention in clinical trials with no reported overt target-related side-effects [15] it was deemed reasonable not to apply any additional margins against MABEL in the first cohort. Furthermore, mPGES-1 -/- mice are viable and fertile and develop normally compared with wild-type controls [18],

hence have no specific phenotype under normal conditions, while being protected in various inflammatory disease models [14].

8.3.2 *Rationale for dose escalation in the SAD part*

The desired pharmacological effect of GS-248 in humans includes i) blocking the production of PGE₂ via mPGES-1, and ii) increased production of the vasodilatory and platelet-inhibitory PGI₂ via substrate shunting. The latter aspect calls for a pronounced level of inhibition of mPGES-1 over 24 h, to optimise for the desired shunting effect and intravascular PGI₂ synthesis.

A PK/exposure-driven dose escalation strategy will be applied such that the first cohort is expected to yield a systemic exposure corresponding to MABEL and the last cohort will achieve exposures close to the maximum exposure limits, as established by the 28-day dog toxicity study, unless safety or tolerability has previously limited escalation. The escalation steps will be smaller when the maximum exposure limits are approached.

Pharmacokinetics will be evaluated following each cohort and the escalation scheme can be modified based on the totality of acquired PK, safety and tolerability data. In case of signs of unpredictable PK (i.e. highly variable or non-linear PK) escalation steps will be decreased. In case the systemic exposure following the first cohort is appreciably smaller than predicted or below the lower limit of quantification (LLOQ), multiple maximum 8-fold dose escalations will be allowed until the exposure is within the predicted range of the study. If the systemic exposure following the first cohort is appreciably larger than projected, escalation steps will be decreased or, in case of limiting safety or tolerability, de-escalation may be performed. The decision on dose selection will be made by the iSRC, which will have access to all safety, tolerability and PK data (8.3.8).

A tentative dose escalation scheme based on target systemic exposures is shown in Table 8.3-2 where the first and last cohorts are determined by MABEL and maximum exposure limits, and the mid-range of maximum attainable AUE₍₀₋₂₄₎ is expected to be achieved between cohort 2 and 3.

Table 8.3-2 Tentative dose escalation schedule SAD

| Cohort: | 1 | 2 | 3 | 4 | 5 | 6 | (7) |
|--------------------------------------|----------|----------|-----------|-------------|-------------|--------------|-------------|
| Tentative dose (mg) | 1 | 5 | 25 | 75 | 225 | 450 | ≤ 800 |
| Predicted AUC_{0-inf} | 19-31 | 97-150 | 480 – 770 | 1500 – 2300 | 4400 – 6900 | 8700 – 14000 | 16000-25000 |

For details on the prerequisites for the transition from single to multiple dosing, refer to Section 8.3.5.

8.3.3 *Selection of starting dose and dose escalation in the MAD part*

The starting dose in the MAD part of the study will be selected with the aim to achieve an exposure similar to that observed in the third cohort in the SAD part, and is tentatively set to 25 mg. The doses in the second and third MAD cohorts will be selected to achieve an

escalation of exposure of approximately 3 times of what was observed in the previous cohort. The dose in the fourth (and potential fifth) MAD cohort will be selected to achieve an exposure twice of what was observed in the previous cohort. Tentative doses are displayed in Table 8.3-3.

Table 8.3-3 Tentative dose escalation schedule MAD

| Cohort: | 1 | 2 | 3 | 4 |
|--|-----------------|----------|----------|------------------|
| Maximum exposure escalation steps | | 3x | 3x | 2x |
| Tentative doses (mg) | 25 ¹ | 75 | 225 | 450 ² |

1. Aimed to achieve an exposure similar to that in the third cohort of the SAD part.
2. Projected exposure not exceeding what was achieved by the study maximum dose given in the SAD part in terms of AUC_{0-∞}.

If the systemic exposure following any of the first 3 cohorts is appreciably larger than projected, escalation steps will be decreased. In case of limiting safety or tolerability, de-escalation may be performed. The decision on dose selection will be made by the iSRC, which will have access to all safety, tolerability and PK data as outlined in Section 8.3.8.

PK information from the SAD part will give the terminal T_{1/2} of the drug, which in turn, will indicate potential accumulation of GS-248. The dose, or dosing interval, will be adjusted accordingly if such is identified. If safety and tolerability allows, the aim is to, in the last MAD cohort, reach a maximum exposure in terms of AUC_{0-tau} not exceeding what was achieved by the study maximum dose given in the SAD part in terms of AUC_{0-∞}.

8.3.4 *Maximum exposure and dose*

The maximum dose to be given is 800 mg/day. The maximum exposure in the study may not exceed 2500 nmol/L or 23 000 h*nmol/L in terms of C_{max} and AUC, respectively, based on C_{max} and AUC₀₋₂₄ at the dog NOAEL (males and females combined).

8.3.5 *From single to multiple dosing*

Following completion of cohort 4 of Part I (SAD), the iSRC will evaluate all available safety, tolerability and PK data up until and including at least 48 h data from SAD cohort 4 and, if necessary, suggest adjustments to dose levels, dosing regimens or dosing duration in a written recommendation to the Sponsor. If no safety or tolerability concerns are identified, and provided that the PK of GS-248 is linear, cohort 1 of Part II (MAD) will be initiated approximately in parallel with cohort 5 of Part I (SAD) as decided by the Sponsor. The predicted exposure in the MAD will not exceed the maximum exposure (based on AUC and C_{max}) in any previously evaluated SAD cohort. The iSRC recommendation, as well as Sponsor's decision, will be documented in a non-substantial amendment to the clinical study protocol (CSP).

8.3.6 *From healthy volunteers to patients*

Prior to start of Part III (SSc patients), a substantial amendment containing a summary of blinded Part I and Part II safety, tolerability and PK data (all cohorts), the intended Part III dose, a dose rationale, the dosing duration and a request to start Part III, will be submitted to

the competent authority (CA) and an independent ethics committee (IEC). In case the systemic exposure of GS-248 is considered sufficiently high already after 3 MAD cohorts, or if indicated by safety and tolerability data, the fourth (and fifth) cohort(s) will not be conducted and the substantial amendment prior to start of Part III will be submitted following completion of the third MAD cohort. Part III will not start until after approval from the CA and IEC.

8.3.7 *Stopping criteria for dose escalation*

The iSRC (including the Principal Investigator; Section 8.3.8) will follow the recommendations and grading system of Common Terminology Criteria for Adverse Events (CTCAE) v5.0 [19] see Section 11.3.1.7 but also take into account the recommendations published by Sibille *et al.* 2010 [20] which is an adaptation to FIH studies of the grading systems previously proposed by National Cancer Institute (NCI) [19], World Health Organization (WHO) [21], National Institute of Health (NIH) [22] and the FDA [23]. The grade, the frequency of AEs and the blindness will be considered.

A rolling review of emerging safety data will be performed throughout the study taking into account any AEs (in particular moderate AEs assessed as at least possibly related to the IMP administration), the number of subjects in whom they occur, concurrency of more than one event within the same subject and any trends. Changes from baseline measurements will also be considered and not just absolute cut-off based on upper- or lower limits of normal that might apply for healthy volunteers.

Trends or safety signals described above, which are not necessarily covered by the stopping criteria in Table 8.3-4 may warrant the scheduling of ad hoc iSRC meetings after which the iSRC will make recommendations to sponsor on e.g. whether to terminate the study or to stop dosing in individual subjects or a certain cohort.

Additional study specific withdrawal criteria are summarised in Section 9.7.

Table 8.3-4 Dose escalation and stopping rules, Part I and Part II

| Stop criterion | Action taken |
|---|---|
| At individual and dose group level | |
| If no subject has an SAE considered at least possibly related to the IMP administration, i.e. a serious adverse drug reaction (SADR) | Escalate to the next higher dose level. |
| If 1 subject on active treatment has an SAE assessed as at least possibly related to IMP administration | 
 1. Stop dosing of subject with a potential SADR. Withdrawal of subject. 2. Unblinding of subject with potential SADR. Only voting members of the iSRC will be unblinded. 3. Evaluation by iSRC. The iSRC makes recommendation to Sponsor. 4. Sponsor decides how to proceed: Subject met stop criterion: stop further dosing at this dose level for all subjects. Sponsor decides if the study will be terminated or if dosing will commence at a lower dose level or at an intermediate dose level. |
| If 2 subjects on active treatment have severe, non-serious AEs assessed at least possibly related to the IMP administration (independent of within or not within the same System organ class [SOC]) | 
 1. Stop dosing of subjects with severe, non-serious potential ADRs. 2. Unblinding of the subjects with potential ADRs. Only voting members of the iSRC will be unblinded. 3. Evaluation by iSRC. The iSRC makes recommendation to Sponsor. 4. Sponsor decides how to proceed: Both subjects meet stop criterion: stop further dosing at this dose level for all subjects. Sponsor decides if the study will be terminated or if dosing should commence at a lower dose level or at an intermediate dose level. |
| If 1 subject has an $AUC_{0-\infty}$ (single dose) or $AUC_{0-\tau}$ (repeated dose) higher than 23 000 h*nmol/L (corresponding to the NOAEL in male and female dogs) ¹ | 
 1. Evaluation by iSRC. The iSRC makes recommendation to Sponsor. 2. Sponsor decides if the study will be terminated or if dosing in the next cohort should commence at a lower dose level or at an intermediate dose level. |
| If 1 subject has a C_{max} higher than 2500 nmol/L (corresponding to the NOAEL in male and female dogs) ¹ | 
 1. Evaluation by iSRC. The iSRC makes recommendation to Sponsor 2. Sponsor decides if dosing in the next cohort should commence at a lower dose level or at an intermediate dose level. |
| Final dosing stop and termination of study | |
| If 2 subjects on active treatment in different cohorts have SAEs assessed as at least possibly related to IMP administration | 
 1. Stop dosing of subjects with potential SADR. Withdrawal of subjects. 2. Unblinding of subjects with potential SADR. Only voting members of the iSRC will be unblinded. 3. Evaluation by iSRC. The iSRC makes recommendation to Sponsor. 4. Subjects meet stop criterion: Termination of study. |

1. When reviewing emerging data in relation to this criterion, the maximum exposure observed in individual subjects within a cohort rather than the mean exposure should be taken into account

8.3.8 *Internal safety review committee*

Before initiating a new cohort, all subjects in the previous cohort must have been treated and safety, tolerability and PK data (at least 48 h data in Part I [SAD] and data up until and including 24 h post last dose in Part II [MAD]) for all treated subjects must have been evaluated by the iSRC.

If GS-248 is considered safe and tolerable, a written recommendation on the next dose level based on the predicted exposure will be provided to the Sponsor. Likewise, the iSRC will recommend dose levels for Part II and III, respectively, based on review of data from earlier cohorts/study parts.

Details regarding timing of iSRC review and the data to be reviewed will be provided in a separate iSRC charter. Based on emerging safety and PK information, the amount of safety and PK data to be reviewed after a completed cohort might be adjusted.

The voting members of the iSRC will consist of the Principal Investigator and the Sponsor's medically responsible person or delegate. In addition, the study clinical research manager (CRM), the study pharmacokineticist, additional Sponsor representatives and further internal or external experts will be invited and consulted as appropriate.

An adaptive dosing strategy will be applied to allow for a flexible and safe dose escalation. The planned dose escalation is outlined in Section 8.3.2 and Section 8.3.3. The actual doses given in each cohort will be guided by the iSRC recommendations based on available safety, tolerability and PK data. Every dose step is thus adjustable and the recommendation to the Sponsor may be to continue with a higher or lower dose than the intended dose, repeat the same dose level, continue with an intermediate dose level or to stop dosing.

The recommendation of the iSRC on the next dose level will be taken in consensus between the iSRC members and documented as appropriate. In case there is disagreement between the 2 voting members, the most conservative approach will be recommended. It is not acceptable to repeat a dose level where any of the dose escalation stopping rules have been met.

In Part I and Part II, 2 or 1 additional cohort(s), respectively, may be added as needed to test additional doses or dosing schemes, repeat the dose given in a previous cohort, to establish the target dose for Part III and subsequent studies and/or to reach steady state. In Part III, 1 additional cohort (10 patients) may be added.

The duration of the residential periods in each part may be amended following review of data from earlier cohorts. The predicted $T_{1/2}$ of GS-248 is between 2 and 13 h, based on allometric scaling of preclinical data. A significantly shorter $T_{1/2}$ than expected, as determined following analysis of PK data in the study, may warrant a shortening of the residential period provided that no safety issues are indicated. Conversely, if indicated by safety and or PK data, the duration of the residential periods may be prolonged. Should the duration of any residential period change, subsequent changes to the timing of safety and PK assessments will be done as necessary. A significantly shorter $T_{1/2}$ than expected may also require a change in the dosing interval, i.e. twice daily GS-248 dosing rather than once daily dosing might be required in order to reach sufficient exposure. Such changes to the CSP (Part I, II or IV with healthy volunteers) will be documented in non-substantial amendments. A substantial amendment will be submitted to both the CA and the IEC prior to start of Part III (SSc patients) of the study, see Section 8.3.6.

The treatment code may be broken by the iSRC during the assessment process (partial unblinding) in accordance with stopping criteria described in Table 8.3-4. The medical staff and the subjects will still be blinded for the treatments (active drug or placebo) to be administered in the subsequent dose groups/cohorts in order to minimise bias. If unblinding was considered necessary, the iSRC meeting will consist of a closed part and an open part.

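### Table 8.3-4 holds human AUC over one dosing interval to a 24-hour dog AUC: correct once daily, but not rescaled for the twice-daily option the protocol allows

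*Protocol*

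**What the plan says.** Section 8.3.1 of the protocol gives the exposure at the NOAEL in the 28-day dog study as Cmax 2500 nmol/L and AUC0-24 23 000 h·nmol/L, and adds: "These values set the maximum limits for exposure in humans in this Phase I study". Note a to Table 8.3-1 confirms that the animal AUC covers 0 to 24 h. Section 8.3.4 caps study exposure at the same two numbers, citing the dog AUC0-24, and caps the dose at 800 mg/day. It does not name the human time window.

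Table 8.3-4 (section 8.3.7) turns the caps into rules applied to the highest individual in a cohort. The AUC row uses AUC0-∞ after a single dose and AUC0-τ in repeated dosing; its repeated-dose part reads "repeated dose) higher than 23 000 h*nmol/L (corresponding to the NOAEL in male and female dogs". A second row fires if one subject's Cmax is "higher than 2500 nmol/L (corresponding to the NOAEL in male and female dogs". The AUC row leads to evaluation by the internal safety review committee (iSRC), after which "Sponsor decides if the study will be terminated or if dosing in the next cohort should commence at a lower dose level" or an intermediate one.

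GS-248 is planned once daily for 10 days (8.1.2). Section 8.3.8 states that the predicted half-life "of GS-248 is between 2 and 13 h, based on allometric scaling of preclinical data", and that a significantly shorter one "than expected may also require a change in the dosing interval", giving twice-daily dosing as the example. For the healthy-volunteer parts such changes "will be documented in non-substantial amendments". Section 8.3.3 also allows the interval to be adjusted if accumulation is found, and 8.3.5 lets the iSRC suggest a different regimen.

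**The concern.** AUC0-τ is exposure over one dosing interval. When the interval is 24 h it can be set directly against a dog AUC0-24. When it is 12 h, the row judges half a day of human exposure against a full day of dog exposure. No section of the protocol scales the limit to the interval.

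This is the only AUC trigger in the table. Its limit comes from the NOAEL in a study where liver and biliary toxicity in dogs set the bound on human exposure (6.4). The liver chemistry criteria in 9.7.3 react once injury shows, whereas an exposure limit is meant to act before that. Section 8.3.3 has the same feature: it ties AUC0-τ in the last multiple-dose cohort to the AUC0-∞ of the highest single dose. With linear kinetics, giving that dose twice a day would satisfy the wording at double the daily AUC.

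**Working it through.** **Inputs.** Dog NOAEL: Cmax 2500 nmol/L, AUC0-24 23 000 h·nmol/L (8.3.1, 8.3.4). Predicted human values at 1 mg: Cmax 4.6–5.6 nmol/L, AUC0-∞ 19–31 h·nmol/L (Table 8.3-1). Predicted half-life 2–13 h (8.3.8). The absorption rate constant ka is in neither document, so it is an assumption, varied from 0.5 to 50/h.

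**Plan's own figures.** The starting-dose margins reproduce: 1400/5.6 = 250 and 9000/31 = 290 against the low dog dose; 2500/5.6 = 446 (stated 450) and 23 000/31 = 742 (stated 740) against the NOAEL. The limits are therefore read correctly.

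**AUC row alone.** The 24 h equivalent of the limit is 23 000 × 24/τ. For τ = 24 h this is 23 000. For τ = 12 h it is 46 000, a factor of 2.0. The correctly scaled limit per 12 h interval would be 23 000 × 12/24 = 11 500.

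**Both rows together.** Let R = AUC0-12/Cmax at steady state. The highest daily AUC that passes both rows is 2 × min(23 000, 2500 × R). This exceeds 23 000 only if R > 11 500/2500 = 4.6 h.

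**When R exceeds 4.6 h.** Assume one compartment, first-order absorption, steady state and k = ln 2/half-life. The concentration is then proportional to ka/(ka − k) × [e^(−kt)/(1 − e^(−kτ)) − e^(−ka·t)/(1 − e^(−ka·τ))], and AUC0-τ to 1/k on the same scale. The table gives the highest unflagged daily AUC as a multiple of 23 000, with τ = 12 h.

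| Half-life | ka 0.5 | 0.75 | 1 | 2 | 50/h | Exceeds 1 only if ka is below |
|---|---|---|---|---|---|---|
| 1 h | 1.00 | 0.82 | 0.72 | 0.55 | 0.33 | 0.50/h |
| 1.5 h | 1.20 | 1.01 | 0.91 | 0.73 | 0.49 | 0.78/h |
| 1.75 h | 1.29 | 1.10 | 0.99 | 0.81 | 0.57 | 0.98/h |
| 2 h | 1.37 | 1.18 | 1.07 | 0.89 | 0.64 | 1.27/h |

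Example: at 2 h and ka = 1/h, R = 4.94 h, and 2 × 2500 × 4.94 is about 24 700, or 1.07 times the limit. The Cmax row has then removed (46 000 − 24 700)/23 000 = 93% of the gap. At ka = 0.5/h it removes 63%.

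**Cross-check on the protocol's prediction.** At 1 mg, AUC/Cmax is 19/4.6 = 4.1 h (low with low) to 31/5.6 = 5.5 h (high with high), on both sides of 4.6 h. These values belong to the predicted half-life range; a shorter half-life would lower them.

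**The case against.** The strongest reply is that the plan as written contains no error. Dosing is once daily, the row is then like for like, and 8.3.1 and 8.3.4 are most naturally read as 24 h caps. A change of interval needs a written, numbered amendment (14.6), where the limit could be restated. The row prompts evaluation, not an automatic stop. Other protections remain: the 800 mg/day cap, predicted AUC and Cmax held within those of earlier single-dose cohorts (8.1.2, 8.3.5), exposure steps of at most 3, 3 and 2 times (8.3.3), pharmacokinetic review after each cohort, and the liver criteria. All of this stands and keeps the point small. It does not remove it: the operative row names τ, neither parent section names the human window, and nothing requires the amendment to restate the limit. Under 14.6 only substantial amendments need outside approval, and 8.3.8 classes this change as non-substantial. The dose cap limits dose, not an individual's exposure. The separate iSRC charter is not available here and may deal with this.

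It can also be said that 2 h is the edge of the trigger case, and that absorption slower than elimination would itself lengthen the observed half-life. That is right. At ka = 0.5/h the terminal half-life would be 0.693/0.5 = 1.39 h, not 1 h. For an observed half-life of 1 h the model gives at most 0.85 times the limit at any absorption rate, and it stays below 1 up to about 1.2 h. The gap therefore needs an observed half-life of roughly 1.2 to 2 h together with slow absorption.

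A reader might go further and scale the 1 mg predictions to 400 mg twice daily: AUC0-12 400 × 31 = 12 400, so 24 800 per day, with Cmax at most 400 × 5.6 = 2240 before accumulation, and conclude that neither row would fire. The documents do not support that as a general result. It pairs the highest predicted AUC with a Cmax predicted for a longer half-life. With AUC0-12 fixed at 12 400, the model gives steady-state Cmax of 2684 to 4901 nmol/L at a 1 h half-life (ka 0.5 to 2/h), and 2510 at 2 h with ka = 1/h. The Cmax row fires in all of these cases.

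**Conclusion.** The point holds as a minor, contingent gap in wording. Once daily there is no effect. Twice daily, the AUC row alone would tolerate 46 000 h·nmol/L per day, twice the dog value. In the case that would prompt the switch, the Cmax row closes most or all of the excess. What remains in the model is at most 1.37 times the limit at a 2 h half-life, and only with slow absorption (ka 0.5/h). These multiples rest on one-compartment linear kinetics, equal 12 h intervals and an assumed absorption range. For half-lives well above 2 h the Cmax row would protect less, but 8.3.8 does not propose twice-daily dosing there.

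A reader might infer that subjects were exposed above the dog limit without a trigger. Nothing supports this. SAP section 3.4 lists multiple doses of 20, 60 and 180 mg and marks only celecoxib as twice daily. At 180 mg the upper predicted AUC is 180 × 31 = 5580; even twice daily it would be 11 160, or 0.49 times the limit.

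**What to change.** In Table 8.3-4, and consistently in 8.3.3 and 8.3.4, state the repeated-dose limit as human steady-state AUC0-24, or equivalently as 23 000 × τ/24 per interval. With equal 12 h intervals AUC0-24 can be taken as 2 × AUC0-12, so no extra samples are needed. Alternatively, add one sentence to 8.3.8 requiring any amendment that changes the dosing interval to restate the limit on a 24 h basis. The cost is a few words, and once-daily dosing is unchanged.
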